Salvage treatment with cystectomy plays an important role in managing patients with chemoradiotherapy and is the gold standard for optimal trimodality therapy should patients relapse. Two approaches here have been reported for patients considered fit for salvage cystectomy. Firstly in the MGH and RTOG protocols, response evaluation is performed after approximately 40Gy of induction therapy [5, 9]. Only complete responders are considered eligible for bladder preservation therapy and proceed with consolidation treatment with the bladder treated up to 64Gy. Conversely, a second alternative is the Erlangen approach [10], where the bladder is evaluated at 4-6 weeks post definitive chemoradiotherapy. The late-response evaluation may theoretically increase the chance of bladder preservation, as some slow responders may still be responding and have not maximally regressed after the 40Gy of treatment. Additionally, split dose radiotherapy is of some concern. However, the two approaches seem equally effective in terms of long term survival and bladder preservation. This study will utilize the latter approach.

An early assessment of efficacy of chemoradiation that is standardly used is the complete response rate, which is determined in most series to be based on first cystoscopic assessment of the bladder cancer 12 weeks after chemoradiotherapy is completed [1, 5]. This involves examination under anesthesia, cystoscopy and biopsy of all previously positive tumor sites that is utilized to evaluate the tumor status (response) following completion chemoradiotherapy. In some patients radiographic or cystoscopic evaluation will reveal abnormalities at the bladder

tumor-site (such as thickening of the wall, ulcerations, or possible nodularities) which contain no identifiable tumor cells histologically. Patients will be considered as having a complete response, or pT0 response, when the bi-manual examination under anesthesia is negative, when all the biopsies are negative for any tumor at the site(s) of the pretreatment tumor(s) and there is an absence of metastatic disease on the most recently performed systemic imaging.

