4.2 Rationale for the combination of pembrolizumab with chemotherapy and radiation

Chemoradiotherapy leads to outcomes similar to cystectomy. However, a significant proportion of patients still fail to achieve a complete response to chemoradiation, require a cystectomy, relapse locally, or develop distant metastatic disease.

Approximately 30% of patients fail to achieve a complete response to therapy, with a relapse rate of 10% with local-regional disease, and 9-20% distant metastatic disease over 2 years [1, 2, 7, 12]. Improvements in these outcomes are desired.

The use of drugs such as pembrolizumab is transforming cancer medicine, and checkpoint inhibitors are resulting in unprecedented disease response rates and longer-term control. However, while a subgroup of bladder cancer demonstrate exquisite responses to these agents, many patients do not derive any benefit. A major challenge therefore is to develop rational strategies by which the activity of these agents can be broadened.

One potential approach is the combination of immunotherapy with radiation therapy. Radiation therapy induced cell killing has the potential to stimulate the release of tumour antigens and trigger antigenic stimulation. Proof of this concept is provided by *in vitro* studies [13], and anecdotally from clinical observations of tumour regressions at unirradiated tumour sites (the abscopal effect). Importantly, the combination of radiotherapy with immune check point inhibitors has been reported to escalate antitumour responses in clinical case reports [14], and shown to be safe when combined with radiation in several trials [15]. The effect of this combination in bladder cancer however has not been extensively investigated.

Predicting the impact of combining chemotherapy with immunotherapy is less straightforward. While chemotherapy may deplete immune effector cells, the cytotoxic effects of chemotherapy may also enhance antigen-release and stimulate immune responses as postulated for radiation therapy. In preclinical mouse models, chemotherapy synergises with anti-PDL1 treatment to

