5.2.6 Evaluations during follow-up

After the end of treatment study visit, patients enter into follow up for OS, LRPFS and DMFS. Follow up for these survival endpoints will be 3 monthly for 12 months after the post treatment review visit, then 6 monthly for 18 months, then 12 monthly until 3 years after the registration of the last patient or study closure. The following assessments will take place at each visit:

1. Vital Signs
2. Directed physical exam
3. Urine cytology
4. Post-study anticancer therapy status
5. Disease Status
6. Survival status

7. Radiological evaluation (CT Chest/Abdo/Pelvis)
8. Cystoscopy assessment

Patients with either local or distant progression do not require vital sign, directed physical examination, urine cytology, or cystoscopy assessment at each visit.

Patients with local progression should continue to receive radiological evaluation for assessment of distant metastatic disease. Patients with distant progression should receive radiological evaluation at the discretion of the investigator.

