7.1.6.2 Follow-Up Visits

The follow-up period will extend for 3 years from the registration of the last patient enrolled. Visits will include clinical assessment, physical assessment, imaging, cystoscopy, urine cytology, documentation of disease status and new anti-cancer therapies and documentation of survival status.

Every effort should be made to collect information regarding disease status until the start of new anti-cancer therapy, detection of metastatic disease determined by the investigator/site and radiologist, death or end of study.

Subjects who have completed the post treatment review visit will move into follow-up and will be assessed until 3 years after registration of the last patient. After the post treatment review visit, follow-up visits will occur as follows:

- 3 monthly for 12 months
- 6 monthly for 18 months
- 12 monthly thereafter for a minimum of 3 years or until study close-out.

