8.3 Methods of analysis

Binary proportions (UT and CR proportions) and their 95% CI's will be provided using the Clopper-Pearson method. Table 10 provides estimates and 95% CI's for various observed counts from a sample size of 30.

Table 10: Estimated proportions and corresponding 95% CI's for a sample size of 30.

Count	Estimate	95% CI
3	0.1	[0.02, 0.27]
6	0.2	[0.08, 0.39]
9	0.3	[0.15, 0.49]
12	0.4	[0.23, 0.59]
15	0.5	[0.31, 0.69]
18	0.6	[0.41, 0.77]
21	0.7	[0.51, 0.85]
24	0.8	[0.61, 0.92]
27	0.9	[0.73, 0.98]

When estimating the UT rate and its 95% CI, the methods of Jung & Kim (2004) and Koyama & Chen (2008) will be used to adjust for the two stage sampling procedure.

It is expected that it will take two years to accrue the required 30 patients. Accrual will not be suspended pending the results of the interim analysis.

OS, DMFS and LRPFS will be characterized using Kaplan-Meier curves.

Both DMFS and LRPFS will be measured from the date of patient registration. DMFS will be measured until the date of first commencement of any non-protocol anti-cancer therapy, detection of distant metastasis, or death due to any cause. LRPFS will be measured until the date of first commencement of any non-protocol anti-cancer therapy, detection of local or regional progression, or death due to any cause. Occurrence of distant metastasis will be a censoring event for measurement of LRPFS. There are no censoring events for DMFS.

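### DMFS counts the start of any non-protocol anti-cancer therapy as an event, so treated local failure enters a curve meant to show metastatic disease-free survival

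*Combined protocol and SAP*

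**What the plan says.** Sections 3.2 and 8.1 name metastatic disease-free survival as a secondary objective. In section 8.3 the clock starts at registration, and the text states that "DMFS will be measured until the date of first commencement of any non-protocol anti-cancer therapy, detection of distant metastasis"; a patient's death, whatever its cause, is the third end point. It adds: "There are no censoring events for DMFS". Section 4.2.4.1 says that the date of new therapy is collected because it belongs to the definitions of both DMFS and LRPFS, so the component is deliberate.

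The companion endpoint is built the same way: "LRPFS will be measured until the date of first commencement of any non-protocol anti-cancer therapy, detection of local or regional progression". Death ends it too, and distant metastasis is a censoring event.

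On what counts as therapy, Table 8 (section 7.1.2.6.2) places intravesical therapy under new anticancer therapies. Section 4.1.2 says: "Salvage treatment with cystectomy plays an important role in managing patients with chemoradiotherapy". It treats cystectomy as the standard recourse at relapse, but no section says outright whether it is a non-protocol anti-cancer therapy.

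On follow-up, section 5.2.6 says: "Patients with local progression should continue to receive radiological evaluation for assessment of distant metastatic disease". Section 7.1.6.2 says: "Every effort should be made to collect information regarding disease status until the start of new anti-cancer therapy", or until metastasis, death or the end of the study. Section 5.7 follows participants for disease status until the study ends or consent is withdrawn.

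**The concern.** The name and the objective point to distant spread, but one of the three events need have nothing to do with it. In bladder preservation, a local failure is commonly followed by local treatment. Nothing in the documents limits the therapy component to treatment of distant disease or exempts local salvage. A patient with a bladder-only recurrence and clean scans who starts intravesical therapy becomes a DMFS event that day. A metastasis found later cannot move that date, although section 5.2.6 continues imaging after local progression in order to look for it.

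DMFS and LRPFS share two of their three components, so a treated local failure is an event in both. A reader who takes the published DMFS curve at its name will see a lower figure than metastasis or death alone would give, and will not be able to tell how much of the gap is local treatment.

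**Working it through.** The plan states no event count, rate or power for DMFS, so there is no figure to reproduce. The definition settles the direction. The size can only be illustrated.

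**Inputs from the documents**
- Failure to reach complete response: "Approximately 30% of patients fail to achieve a complete response to therapy" (section 4.2).
- Locoregional relapse 10%, and distant metastasis (DM) 9-20% over 2 years (section 4.2).
- N = 30 (section 8.2).

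**Assumptions, not in the documents**
- The 10% relapse applies to the 70% who responded: local failure L = 0.30 + 0.10 × 0.70 = 0.37.
- Local failure is independent of DM.
- s is the share of purely local failures who start non-protocol therapy; 50% and 100% are shown.
- Deaths without metastasis are left out of both versions.

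**Formulas at 2 years**
- Therapy-only events = 30 × s × L × (1 − DM)
- Event-free, metastasis only = 1 − DM
- Event-free, as written = 1 − DM − s × L × (1 − DM)

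| s | DM | Therapy-only events | Metastases | Event-free, metastasis only | Event-free, as written |
|---|---|---|---|---|---|
| 50% | 9% | 30 × 0.5 × 0.37 × 0.91 = 5.1 | 2.7 | 91% | 74% |
| 50% | 20% | 30 × 0.5 × 0.37 × 0.80 = 4.4 | 6.0 | 80% | 65% |
| 100% | 9% | 30 × 0.37 × 0.91 = 10.1 | 2.7 | 91% | 57% |
| 100% | 20% | 30 × 0.37 × 0.80 = 8.9 | 6.0 | 80% | 50% |

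In these four cases the estimate as written is lower by 15 to 34 points.

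**Varying the assumptions.** L was taken from 30% to 40% (the simple sum), s from 50% to 100%, and the overlap from none to every metastatic patient also failing locally.
- Smallest effect: DM 20%, L 30%, s 50%, full overlap. 0.5 × (0.30 − 0.20) = 0.05, which is 1.5 patients, 5 points, and 0.05/0.25 = 20% of the events counted.
- Largest effect: L 40%, s 100%, no overlap. 0.40, which is 12 patients and 40 points. At DM 9% that is 0.40/0.49 = 82% of the events counted.

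**Cross-check.** In the table of published series in section 4.1.2, overall survival exceeds the BIS column by 8 to 18 points where both are given (at 5 years, or 4 years in one series). That is 2.4 to 5.4 of 30 patients. If BIS means bladder-intact survival (an assumption), bladder loss in surviving patients is common enough to matter. Those patients need not all be free of metastasis, so this supports the order of size only.

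**The case against.** Counting new therapy as an event is a prespecified composite, stated consistently in sections 4.2.4.1 and 8.3. DMFS carries no threshold, power or decision rule. Section 3.2 already lists the dates of death, metastasis, locoregional progression and new therapy separately, so a metastasis-or-death curve could be drawn if disease status continues to be recorded. All of this stands. It limits the weight of the point but does not make the curve match its objective.

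Several stronger readings are tempting, and the documents do not support them:
- **That 8.3 contradicts 5.2.6.** It does not. Local progression is not itself a DMFS event, so scans still count for a locally progressed patient who has not started new therapy. The mismatch is one of purpose, and it begins when therapy begins.
- **That 7.1.6.2 orders disease-status collection to stop at new therapy.** It sets a minimum effort. Section 5.7 carries on to study end, and section 7.1.1.5.3 moves such patients into follow-up. The wordings still need reconciling, because a site working from 7.1.6.2 alone might stop recording.
- **That cystectomy is expressly an event.** Only intravesical therapy is explicit. Cystectomy is covered by ordinary reading, helped by section 7.1.1.5.2, which lists surgeries among prior cancer treatments.
- **That DMFS is mainly a measure of local failure, or no longer describes metastasis at all.** Metastasis remains a component. The therapy-only share runs from 20% to 82% before deaths are counted, and the treated share has no source. Complete response as defined requires absence of metastasis, so non-responders include some metastatic patients, and overlap lowers the count. Eligibility also admits patients unsuitable for cystectomy.
- **That a systemic effect of pembrolizumab would be hidden.** One uncontrolled arm of 30 patients, described by Kaplan-Meier curves, is not set up to show one. Nor could a metastasis-or-death curve be set directly beside the published metastasis rates, since it counts deaths too.

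**Conclusion.** The point holds as a fault in how the endpoint is built. As written, DMFS mixes treated local failure with distant metastasis and death, overlaps with LRPFS, and cannot be read as metastatic disease-free survival. The direction is certain: any metastasis-free patient who starts such therapy for a local failure lowers the curve. The size is not certain, because it rests on the treated share, on how local and distant failure overlap, and on leaving out deaths, which are events under either definition. The central illustration is about 4 to 10 therapy-only events in 30 patients; even the smallest variant tried removes about 5 points at 2 years. The unacceptable-toxicity decision, the complete-response rule and the sample size do not change.

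**What to change.** - In section 8.3, define DMFS as time from registration to first distant metastasis or death from any cause. Follow patients through non-protocol therapy, and censor those without an event at their last disease assessment. The statement that there are no censoring events should go, since patients who are event-free at the end need a censoring rule.
- Report the present definition as a supplementary composite under another name, and state whether salvage cystectomy counts as non-protocol anti-cancer therapy in it. Bring section 4.2.4.1 into line.
- Reconcile section 7.1.6.2 with sections 5.2.6 and 5.7, so that distant-metastasis status is recorded until metastasis, death or study end.

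The cost is a few sentences. Imaging after local progression and the date of new therapy are already in the plan, and no change to sample size, treatment or visit schedule follows. The wording in 7.1.6.2 should be settled early, because metastases that go unrecorded after salvage may not be recoverable. The downside is that some metastases will be detected after salvage systemic therapy, which may have altered their timing; the supplementary composite shows this.

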5.7 Participant Withdrawal/Discontinuation Criteria

Participants may withdraw consent at any time for any reason or be dropped from the trial at the discretion of the investigator should any untoward effect occur. A patient who withdraws consent prior to commencement of pembrolizumab and chemoradiotherapy may be replaced to ensure 30 patients in total are treated with the combination. In addition, a participant may be withdrawn by the investigator or the Sponsor if enrolment into the trial is inappropriate, the trial plan is violated, or for administrative and/or other safety reasons. Specific details regarding discontinuation or withdrawal are provided in Section 7.1.4– Other Procedures.

A participant must be discontinued from trial treatment for any of the following reasons:

- Confirmed radiographic locoregional or metastatic disease progression
- Initiation of new anti-cancer therapies
- Intercurrent illness that prevents further administration of treatment
- Investigator's decision to withdraw the participant
- The participant has a confirmed positive serum pregnancy test
- Noncompliance with trial treatment or procedure requirements
- The participant is lost to follow-up
- Administrative reasons
- The participant or legal representative (such as a parent or legal guardian) withdraws consent.
- Patient decision to withdraw

The End of Treatment and Follow-up visit procedures are listed in Section 6 (Protocol Flow Chart) and Section 5.2.6 (Evaluations during follow-up)

After the end of treatment visit, each participant will be followed as per the follow-up schedule outlined in Section 5.2.6. Participants will be followed until end of study or until withdrawal of consent, for disease status, initiation of new anticancer therapies, and overall survival.

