8.5 Timing of Analyses

A total of three analyses will be performed.

1. The interim analysis for the primary objective (feasibility) will take place after the 10th patient has reached the 31 week assessment time point.
2. Provided that the interim analysis does not result in the trial being closed prematurely due to unacceptable toxicity, the final analysis for the primary objective will take place after the last patient has reached the 31 week assessment time point.
3. Provided that the interim analysis does not result in the trial being closed prematurely due to unacceptable toxicity, the analysis for the secondary efficacy objectives, as well as the analysis of any exploratory objectives, will take place after the last patient has reached 3 years past registration.

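### LRPFS counts death and new therapy as events but is censored at distant metastasis, so its Kaplan-Meier curve overstates the chance of being free of those events

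*Combined protocol and SAP*

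**What the plan says.** Section 8.3 measures LRPFS from registration to the first of new non-protocol anti-cancer therapy, "detection of local or regional progression, or death due to any cause". The rule that follows is "Occurrence of distant metastasis will be a censoring event for measurement of LRPFS". The same section says that distant metastasis-free survival (DMFS), which shares the therapy and death components, has no censoring events. The method is stated in one line: "OS, DMFS and LRPFS will be characterized using Kaplan-Meier curves". It gives no reason for the censoring rule and names no competing-risks method or sensitivity analysis. Nor does it say that LRPFS is meant as a hypothetical quantity in which metastasis does not occur.

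Three other places bear on this:

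- Section 5.7, on follow-up after treatment ends: "Participants will be followed until end of study or until withdrawal of consent, for disease status, initiation of new anticancer therapies, and overall survival".
- Section 5.2.6, on what is no longer checked: "Patients with either local or distant progression do not require vital sign, directed physical examination, urine cytology, or cystoscopy assessment at each visit"; and "Patients with distant progression should receive radiological evaluation at the discretion of the investigator".
- Section 8.5: the efficacy analysis "will take place after the last patient has reached 3 years past registration".

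**The concern.** Kaplan-Meier assumes that a censored patient has the same later risk of the event as a patient still under observation. That is hard to accept here. Metastasis is likely to bring forward two of the three listed events, new therapy and death. Censoring at metastasis takes high-risk patients out of the risk set just before they fail and lets lower-risk patients stand in for them. In effect, death from any cause becomes death without prior metastasis.

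A reader will take the curve as the chance of being alive without locoregional progression or new therapy. With no control arm, that figure will be compared with published series at face value.

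The rule also accounts for much of the censoring. At the efficacy analysis every patient is at least 3 years past registration. Before 3 years, metastasis is therefore the main reason for censoring, apart from withdrawal or loss to follow-up.

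**Working it through.** The plan states no LRPFS figure, so there is none to reproduce. The question is how far the curve as written lies above the probability of being free of the listed events.

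**Hand count.** Take 30 patients followed for 2 years. Two have a listed event before month 12. Five are found to have metastases at month 12, and four of these later die or start therapy. Two patients without metastasis have an event after month 12.

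- As written: 28/30 × 21/23 = 85.2%. The five leave the risk set, 28 − 5 = 23.
- Counting every listed event: 2 + 2 + 4 = 8 failures, so 22/30 = 73.3%.
- With three metastases, two of them followed by an event: 28/30 × 23/25 = 85.9%, against 24/30 = 80.0%.

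**Closed form, immediate detection.** Inputs from section 4.2: "with a relapse rate of 10% with local-regional disease, and 9-20% distant metastatic disease over 2 years". Assumed, because the documents do not give them: 5% other deaths by 2 years, 12-month median survival after metastasis, and 70% of metastatic patients starting systemic therapy 1.5 months after it. Hazards are constant. D is the monthly hazard of metastasis and m = ln 2/12.

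- As written: S = 0.90 × 0.95 = 0.855.
- Uncensored: S × [exp(−24D) + ∫₀²⁴ D·exp(−Dt)·exp(−m(24−t))·g(24−t) dt], where g(u) = 1 for u < 1.5 and 0.3 otherwise.
- 9% distant: 0.855 × (0.910 + 0.0181) = 0.793, an excess of 6.2 points.
- 20% distant: 0.855 × (0.800 + 0.0392) = 0.718, an excess of 13.8 points.

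**Visit-based detection.** This simulation uses the same hazards. Progression is found only at weeks 19 and 31, then 3, 6, 9, 12, 18, 24, 30 and 42 months later. Local progression after detected metastasis is not counted.

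| Case | Excess, 9% distant | Excess, 20% distant |
|---|---|---|
| 2 years, immediate detection | 6.2 | 13.8 |
| 2 years, protocol visits | 4.9 (86.6% v 81.7%) | 10.8 (85.5% v 74.7%) |
| 2 years, visits, 30% also start early local therapy | 3.4 | 7.5 |
| 2 years, visits, 18% locoregional (section 4.1.1) | 4.5 | 10.0 |
| 3 years, immediate detection | 8.9 | 19.3 |
| 3 years, protocol visits | 7.2 | 15.4 |

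In the base visit case, 1.8 and 4.1 of 30 patients are censored at metastasis by 2 years. Of these, 1.6 and 3.5 have a later listed event by 2 years that is dropped.

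**Bounds that need no assumption about the time after metastasis** (2 years, 10% locoregional, immediate detection). If metastasis adds no risk, the excess is 0. If every metastatic patient fails at once, it is 0.855 × 0.09 = 7.7 points or 0.855 × 0.20 = 17.1 points.

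**Second model.** This is an illness-death model with constant yearly hazards: a for a listed event before metastasis, m for metastasis (here per year) and b for a listed event after it. As written, the curve tends to exp(−at). The event-free probability is exp(−(a+m)t) + m·exp(−bt)·[1 − exp(−(a+m−b)t)]/(a+m−b). With 10-30% listed events by 2 years without metastasis and b from 0.7 to 3.0 per year, the 2-year excess is 2.4-6.8 points at 9% metastasis and 5.5-15.2 points at 20%. Setting b = a gives zero.

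**The case against.** The strongest reply is that this is an openly stated definition. The contrast with DMFS suggests a deliberate wish to keep distant failure out of a locoregional endpoint. Section 5.2.6 stops routine cystoscopy after distant progression. Section 7.1.6.2 asks for disease status only until metastasis, new therapy, death or study end. Metastases are counted in DMFS and all deaths in OS. On this view only a label is missing.

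Part of this stands. Those sections give a sound reason to stop assessing local status at metastasis. They give none for discarding deaths and new therapies, which are still followed. Reporting these patients in DMFS or OS does not correct the LRPFS curve. A hypothetical no-metastasis reading would need independent censoring, which is implausible here, and section 8.3 does not claim it.

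Two points on size also stand. First, section 4.2 says about 30% of patients do not reach complete response. If many of them have early local therapy, the 3-8 point row is the more relevant one. Second, part of the excess is treatment of metastasis: with no post-metastasis therapy, the 2-year closed-form excess falls to 3.6 and 8.1 points. Sampling error also matters at n = 30. The SD of the 2-year estimate is 6.3-6.7 points, about the size of the bias. The bias does not average out, though: in simulated trials of 30 on the visit schedule, the written rule gave the higher value in 80% (9% distant) and 98% (20% distant), and the lower in 3% and 1%.

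**Conclusion.** The concern holds. As written, the LRPFS curve is not the probability of being free of the events that section 8.3 lists, and it reads too high whenever the risk of death or new therapy rises after metastasis. The documents do not state that rise, but it is the natural expectation.

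The size is illustrative. On section 4.2's rates and the stated assumptions, it is about 5-11 points at 2 years on the visit schedule, 3-8 points with frequent early local therapy, and larger at 3 years. The toxicity and complete-response rules are unaffected. LRPFS is a descriptive secondary endpoint with no test or threshold, so this should be corrected before the efficacy analysis but does not threaten the trial's main conclusion.

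**What to change.** In section 8.3, delete the rule that censors LRPFS at distant metastasis. Count deaths and new therapies that follow metastasis, and note that local progression after it may be missed because cystoscopy is no longer required.

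If a purely locoregional measure is wanted, replace the censored Kaplan-Meier curve with the cumulative incidence of locoregional progression, treating metastasis first, death and new therapy as competing events. In that case local therapy for persistent bladder disease should not be hidden among the competing events. Count it as local failure or show it as a separate category, and say which. State which of the two quantities LRPFS is meant to be.

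The cost is one or two sentences and minor programming. Dates of death, metastasis, locoregional progression and new therapy are already endpoints (section 3.2). The drawback of the first option is a less favourable figure that partly reflects treatment of metastasis. The cumulative-incidence option avoids that.
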